3.3 Inclusion of Women and Minorities

Both men and women of all races and ethnic groups are eligible for this trial.

4. REGISTRATION PROCEDURES

4.1 General Guidelines for DF/HCC Institutions

Institutions will register eligible participants in the Clinical Trials Management System (CTMS) OnCore. Registrations must occur prior to the initiation of protocol therapy. Any participant not registered to the protocol before protocol therapy begins will be considered ineligible and registration will be denied.

An investigator will confirm eligibility criteria and a member of the study team will complete the protocol-specific eligibility checklist.

Following registration, participants may begin protocol therapy. Issues that would cause treatment delays should be discussed with the Overall Principal Investigator (PI). If a participant does not receive protocol therapy following registration, the participant's registration on the study must be canceled. Registration cancellations must be made in OnCore as soon as possible.

4.2 Registration Process for DF/HCC Institutions

DF/HCC Standard Operating Procedure for Human Subject Research Titled *Subject Protocol Registration* (SOP #: REGIST-101) must be followed.

5. TREATMENT PLAN

5.1 Treatment Regimen

One cycle is defined as 28 consecutive days. Participants will receive durvalumab and tremelimumab both via IV infusion on day 1 of each cycle. Participants will receive tremelimumab for up to 4 cycles (4 doses). Beginning with cycle 5 day 1, participants will continue to receive durvalumab alone (as monotherapy).

Treatment will be administered on an outpatient basis. Reported adverse events and potential risks are described in **Section 7**. Appropriate dose modifications are described in **Section 6**. No investigational or commercial agents or therapies other than those described below may be administered with the intent to treat the participant's malignancy, with the exception of palliative

radiation therapy or surgical resection to non-target lesions. Bisphosphonate use is permitted.

5.2 Duration of Treatment and Criteria for Retreatment

Participants who are tolerating durvalumab monotherapy without evidence of disease progression per modified RECIST criteria for mesothelioma may continue to receive durvalumab as monotherapy indefinitely or until other criteria for discontinuation are met (see Section 5.6).

Participants experiencing either confirmed or unconfirmed PD during the durvalumab monotherapy portion of the trial may undergo retreatment with tremelimumab (once only) if they meet the retreatment criteria below. The same treatment guidelines followed during the initial treatment period will be followed during the retreatment period, including the same dose and frequency of treatments and the same schedule of assessments, with the exception that participants undergoing retreatment are not required to undergo additional tumor biopsies.

- 1. The patient has not received any other anticancer treatments for their disease (with the exception of palliative radiation or surgical procedures as allowed per protocol).
- 2. The patient does not meet any of the other investigational product discontinuation criteria (Section 5.6).
- 3. Absence of clinical symptoms or signs indicating clinically significant disease progression.
- 4. No decline in ECOG performance status compared to baseline.
- 5. Absence of rapid PD or threat to vital organs/critical anatomical sites (e.g., spinal cord compression) requiring urgent alternative medical intervention.
- 6. All AEs while receiving initial therapy must have resolved to ≤ Grade 1 or baseline. Must not have experienced a ≥ Grade 3 AE, or pneumonitis or neurologic AE of any grade while receiving initial therapy. Note: Subjects with an endocrine AE of any grade are permitted to be retreated if they are stably maintained on appropriate replacement therapy and are asymptomatic.
- 7. Must not have used additional immunosuppression other than corticosteroids for the management of an AE, must not have experienced recurrence of an AE if rechallenged, and not currently requiring maintenance doses > 10 mg prednisone or equivalent per day.
- 8. The patient has had a tumor imaging assessment within 28 days of restarting their assigned treatment; all further scans should occur with the same frequency as during the initial treatment period (relative to the date of registration) until study treatment is stopped.

During the retreatment period, patients may resume tremelimumab dosing at 75 mg once every 4 weeks for 4 doses while continuing to receive durvalumab once every 4 weeks. Patients will then continue with durvalumab monotherapy at 1500 mg once every 4 weeks, beginning 4 weeks after the last dose of combination therapy.

Treatment through progression is at the treating investigator's discretion, and the treating investigator should ensure that patients do not have any significant, unacceptable, or irreversible toxicities that indicate that continuing treatment will not further benefit the patient. A patient

with a confirmed progression receiving durvalumab plus tremelimumab cannot continue therapy or obtain retreatment if dosing is ongoing in the combination portion of therapy and progression occurs in a target lesion that has previously shown a confirmed response. Patients who the Overall PI (in communication with AstraZeneca) and/or the treating investigator determine may not continue treatment will enter follow-up.

Subjects should be made aware of the potential benefits and risks of continuing study regimens in the setting of confirmed or suspected PD leading to retreatment by providing separate written informed consent. Subjects will only be eligible for one retreatment opportunity.

5.3 Pre-Treatment Criteria

5.3.1 Cycle 1, Day 1

Patients who completed screening assessments >72 hours prior to cycle 1 day 1 must have cycle 1 day 1 laboratory values that re-meet eligibility criteria. If screening assessments were completed \leq 72 hours prior to cycle 1 day 1, laboratory tests do not need to be repeated on cycle 1 day 1 and the screening laboratory values can be used as the cycle 1 day 1 values.

If patients have cycle 1 day 1 labs performed, review of results by the treating investigator prior to dosing is required for the following tests: complete blood count with differential (CBC), blood urea nitrogen (BUN), serum creatinine, electrolytes, and liver function tests.

5.3.2 Subsequent Cycles

Management of specific toxicities considered at least possibly related to tremelimumab and/or durvalumab are outlined in **Section 6**.

5.4 Agent Administration

Table 1: Treatment Regimen Description					
Agent	Premedications/ Precautions	Dose	Route	Schedule	Cycle Length
Tremelimumab	None	75 mg	IV over 1 hour (± 5 min) Administer prior to durvalumab	Day 1 for 4 cycles	28 days (4 weeks)
Durvalumab	None	1500 mg	IV over 1 hour (± 5 min) Begin infusion 1 hour after	Day 1	*

completion of	
tremelimumab (±	
10 min)	

5.4.1 Tremelimumab

Tremelimumab will be administered first. Participants will receive 75 mg tremelimumab via IV infusion on day 1 of each cycle for up to 4 cycles (once every 4 weeks for up to 4 doses). Tremelimumab should be infused over 1 hour; there is a \pm 5 minute infusion window. Tremelimumab will be administered at room temperature by controlled infusion via an infusion pump into a peripheral or central vein. Following preparation of tremelimumab, the entire contents of the IV bag should be administered as an IV infusion using a 0.2 or 0.22-µm in-line filter.

The IV line should be flushed with a volume of IV solution (0.9% saline) equal to the priming volume of the infusion set used after the contents of the IV bag are fully administered, or complete the infusion according to institutional policy to ensure the full dose is administered.

5.4.2 Durvalumab

Participants will receive 1500 mg durvalumab via IV infusion on day 1 of each cycle (once every 4 weeks). Durvalumab infusion will start 1 hour after the end of the tremelimumab infusion (± 10 minute window). Durvalumab should be infused over 1 hour; there is a ± 5 minute infusion window. Durvalumab will be administered at room temperature by controlled infusion via an infusion pump into a peripheral or central vein. Following preparation of durvalumab, the entire contents of the IV bag should be administered as an IV infusion using a 0.2 or 0.22-µm in-line filter.

The IV line should be flushed with a volume of IV solution (0.9% saline) equal to the priming volume of the infusion set used after the contents of the IV bag are fully administered, or complete the infusion according to institutional policy to ensure the full dose is administered.

5.4.3 Post-Infusion Observation Period

A 1 hour observation period is required after the completion of the first infusions of both durvalumab and tremelimumab (± 10 minute window). If no clinically significant infusion reactions are observed during or after the first infusions, subsequent infusion observation periods can be at the treating investigator's discretion (suggested 30 minutes after each durvalumab and tremelimumab infusion).

5.5 General Concomitant Medication and Supportive Care Guidelines

The treating investigator must be informed as soon as possible about any medication taken from the time of screening until the end of the clinical phase of the study (final study visit). Any concomitant medication(s), including herbal preparations, taken during the study will be recorded in the CRF.

Restricted, prohibited, and permitted concomitant medications are described in the following tables.

5.5.1 Permitted concomitant medications

Investigators may prescribe concomitant medications or treatments (e.g., acetaminophen, diphenhydramine) deemed necessary to provide adequate prophylactic or supportive care except for those medications identified as "excluded" as listed in **Section 5.5.2**.

5.5.2 Excluded Concomitant Medications

The following medications are considered exclusionary during the study:

- 1. Any investigational anticancer therapy other than the protocol specified therapies
- 2. Any concurrent chemotherapy, radiotherapy (except palliative radiotherapy), immunotherapy, biologic, or hormonal therapy for cancer treatment, other than any stated protocol specified therapies. Concurrent use of hormones for noncancer-related conditions (e.g., insulin for diabetes and hormone replacement therapy) is acceptable. Local treatment of isolated lesions for palliative intent is acceptable (e.g., by local surgery or radiotherapy). Bisphosphonate use is permitted.
- Immunosuppressive medications including, but not limited to systemic corticosteroids at doses exceeding 10 mg per day, methotrexate, azathioprine, and TNF-α blockers. Use of immunosuppressive medications for the management of investigational product-related AEs or in subjects with contrast allergies is acceptable. In addition, use of inhaled, topical, ophthalmic, and intranasal corticosteroids is permitted, along with local steroid injections.
- 4. Live attenuated vaccines within 30 days of durvalumab and tremelimumab dosing (i.e., 30 days prior to the first dose, during treatment with durvalumab and tremelimumab, and for 30 days post discontinuation of durvalumab and tremelimumab). Inactivated vaccines, such as the injectable influenza vaccine, are permitted.

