11.1.2 Disease Parameters

Measurable disease. Measurable lesions are defined as those that can be accurately measured in at least one dimension of at least 10 mm in diameter or thickness with CT scan, MRI, or calipers by clinical exam. All tumor measurements must be recorded in millimeters (or decimal fractions of centimeters).

Note: Tumor lesions that are situated in a previously irradiated area might or might not be

considered measurable.

Malignant lymph nodes. To be considered pathologically enlarged and measurable, a lymph node must be ≥ 15 mm in short axis when assessed by CT scan (CT scan slice thickness recommended to be no greater than 5 mm). At baseline and in follow-up, only the short axis will be measured and followed.

Non-measurable disease. All other lesions (or sites of disease), including small lesions (longest diameter <10 mm or pathological lymph nodes with \geq 10 to <15 mm short axis), are considered non-measurable disease. Bone lesions, leptomeningeal disease, ascites, pleural/pericardial effusions, lymphangitis cutis/pulmonitis, inflammatory breast disease, abdominal masses (not followed by CT or MRI), and cystic lesions are all considered non-measurable.

Note: Cystic lesions that meet the criteria for radiographically defined simple cysts should not be considered as malignant lesions (neither measurable nor non-measurable) since they are, by definition, simple cysts.

'Cystic lesions' thought to represent cystic metastases can be considered as measurable lesions, if they meet the definition of measurability described above. However, if non-cystic lesions are present in the same participant, these are preferred for selection as target lesions.

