11.1.4 Response Criteria

11.1.4.1 Evaluation of Target Lesions

Complete Response (CR): Disappearance of all target lesions. Any pathological lymph nodes (whether target or non-target) must have reduction in short axis to <10 mm.

Partial Response (PR): At least a 30% decrease in total tumor measurement.

Progressive Disease (PD): At least a 20% increase in the total tumor measurement, taking as reference the smallest sum on study (this includes the baseline sum if that is the smallest on study). In addition to the relative increase of 20%, the sum must also demonstrate an absolute increase of at least 5 mm. (Note: the appearance of one or more new lesions is also considered progressions).

Stable Disease (SD): Neither sufficient shrinkage to qualify for PR nor sufficient increase to qualify for PD, taking as reference the smallest sum diameters while on study.

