13. STATISTICAL CONSIDERATIONS

We will employ a Simon's 2-stage design to test the hypothesis that durvalumab and tremelimumab improve response rates in this patient population to 35%, compared to a historical control rate of 16%. In the first stage we will enroll 19 patients, and if 4 or more patients among those 19 respond to therapy (with either a complete or partial response), we will open the 2nd stage of accrual to enroll an additional 21 patients, making a total sample size of 40 patients. If fewer than 4 patients experience a response in the first stage then the study will be stopped. In order to declare study success, a total of 10 or more responses must be observed among all 40 study participants. This design has a 0.64 probability of stopping early under the null, and has 90% power while maintaining an overall one-sided type I error rate of 0.08.

Statistical Analysis Plan for Correlative Studies:

Data from correlative studies will be summarized using descriptive statistics. Associations

between immune cell subsets, immune marker expression, and the characteristics of the PBMCs will be compared to clinical outcome, will be summarized by descriptive methods, and may be explored graphically.

We assume that 80% of patients (n=32) will be successfully biopsied at multiple time points and have tumors that yield valid results from the laboratory.

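### Sections 5.1 and 5.5.2 set different limits on local treatment of lesions, and no response rule in the protocol keeps shrinkage of a resected or irradiated target lesion out of the primary ORR.

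*Combined protocol and SAP*

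**What the plan says.** **Local treatment.** Section 5.1 bars any other treatment aimed at the malignancy, except palliative "radiation therapy or surgical resection to non-target lesions". Section 5.5.2 excepts palliative radiotherapy from its list of exclusions and adds: "Local treatment of isolated lesions for palliative intent is acceptable (e.g., by local surgery or radiotherapy"). It does not mention target or non-target lesions. The retreatment criteria in Section 5.2 refer only to procedures the protocol allows, which does not settle the matter.

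**Response.** Section 11.1.4.1 defines PR as "At least a 30% decrease in total tumor measurement", with no condition on how the decrease arose. Section 11.1.4.4 makes best overall response depend on measurement and confirmation, over the period from start of treatment to progression. Section 11.1.7 has the scans read centrally. Section 13.4.2 assesses every eligible participant for response, including those with major deviations from protocol therapy.

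**Decision rule.** Section 13: "In the first stage we will enroll 19 patients, and if 4 or more patients among those 19 respond to therapy", the second stage opens. For success, "a total of 10 or more responses must be observed among all 40 study participants". The design, with a null rate of 16% and a target rate of 35%, "has 90% power while maintaining an overall one-sided type I error rate of 0.08".

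**The concern.** The two treatment sections can be read to different effect. A site working from 5.5.2 could arrange palliative surgery on a target lesion that 5.1 does not allow. For radiotherapy the position depends on how 5.1 is parsed. If the non-target limit covers radiotherapy, 5.1 and 5.5.2 differ again. If it covers surgery only, neither section bars irradiation of a target lesion.

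The statistical problem comes after that. Once a target lesion has been removed or irradiated, a fall in the sum no longer measures drug effect, yet the written PR rule still counts it. A single-arm trial has no control group in which the same artefact would appear, and the verdict rests on one response count with a threshold at each stage. A few miscounted patients, or one, can change the result.

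**Working it through.** **1. Does any rule stop the miscount?** Each candidate in the protocol text was checked:

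- PR definition (11.1.4.1): a threshold on the total, with no exception for local treatment.
- Confirmation (11.1 and Table 8): a resected lesion is still absent at the next scan, so confirmation is met.
- Response window (11.1.4.4): closed by progression, not by local treatment.
- Central reading (11.1.7): applies the written criteria, which are silent on this.
- Deviations (13.4.2): the patient is still assessed, so a breach of 5.1 does not by itself remove the response.
- Radiation provisions: eligibility criterion 3.1.4 concerns radiation to the only measurable site and, as an entry criterion, radiation before the study. The note in 11.1.2 ("Tumor lesions that are situated in a previously irradiated area might or might not be" considered measurable) concerns measurability in previously irradiated areas.

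None of them prevents it.

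**2. When can it happen?** If the rest of the sum is unchanged, complete removal of a lesion lowers the total by that lesion's share, so the share must be at least 30%. Irradiation that only shrinks the lesion needs a larger share. The fall must also be recorded before progression.

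**3. Reproduce the design.** Inputs from Section 13: n1 = 19, continue with 4 or more responses; n2 = 21, success with 10 or more of 40; p0 = 0.16, p1 = 0.35. With b the binomial probability:

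- Early stopping = P(X1 ≤ 3 | 19, p).
- P(success) = Σ over x ≥ 4 of b(x; 19, p) × P(X2 ≥ max(0, 10 − x) | 21, p).

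| Quantity | Stated | Computed |
|---|---|---|
| Early stopping at 0.16 | 0.64 | 0.638 |
| Type I error at 0.16 | 0.08 | 0.082 |
| Power at 0.35 | 0.90 | 0.901 |

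The stated figures reproduce.

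**4. One false PR (illustration).** One patient is counted as a responder regardless; the other 39 respond at 16%.

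- In stage 1: at least 3 of the other 18 must respond to continue, and at least 9 of the other 39 for success. Type I error = 0.149.
- In stage 2: at least 4 of 19 to continue, and at least 9 of the other 39 for success. Type I error = 0.131.

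**5. A false-PR rate (assumed).** If a share q of true non-responders is miscounted, the apparent null rate is p = 0.16 + 0.84q.

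| q | p | Early stopping | Type I error |
|---|---|---|---|
| 0 | 0.1600 | 0.638 | 0.082 |
| 1% | 0.1684 | 0.599 | 0.107 |
| 2% | 0.1768 | 0.560 | 0.137 |
| 2.5% | 0.1810 | 0.540 | 0.153 |
| 5% | 0.2020 | 0.446 | 0.247 |

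The documents give no rate of on-study local treatment, so every q above zero is an assumption.

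**The case against.** The strongest reply is that 5.1 is a specific prohibition with a named exception, while 5.5.2 is a general list that says nothing on target status. Read together, both apply, and resecting a target lesion breaches 5.1. This is a fair reading for surgery. It leaves radiotherapy open, and it does not help the endpoint, because 13.4.2 still assesses patients with major deviations.

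Second, 13.4.2 offers a category for unknown or not assessable response, so the central reader is not forced to record PR. That is true, but nothing says when the category applies, and a resected lesion leaves a measurable total that meets the PR threshold.

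Third, the modified RECIST guideline is adopted by citation and may deal with treated lesions. It could not be checked here. The point is limited to what the protocol itself states.

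Fourth, the pathway is narrow. The pleural measure adds six thickness measurements, bone lesions are not measurable, and treatment after progression cannot create a responder. All of this stands, and it limits how often the problem could arise.

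A reader might also infer that the 11.1.2 note on irradiated areas lets on-study radiation shrinkage count. It does not: it bears on whether a lesion is measurable and is not a scoring rule. And a reader might lower both thresholds by one, giving 0.143 (final only) or 0.169 (both stages). That adds a false responder on top of 40 ordinary patients. Replacing one of the 40 gives the smaller figures used here.

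**Conclusion.** The point holds in a limited form. Sections 5.1 and 5.5.2 differ on surgery to target lesions under either reading, and on radiotherapy under one. The protocol's response rules would count shrinkage caused by local treatment of a target lesion as a confirmed PR.

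A single such case would raise the type I error from 0.082 to between 0.131 and 0.149. Rates of 1% to 2.5% would raise it to between 0.107 and 0.153. These figures are conditional: they assume that the miscount occurs, that the remaining patients respond at the null rate, and, for the rates, that q applies equally to all true non-responders. It would be tempting to conclude that the trial's actual type I error is near 0.15. The documents do not support that, because they give no frequency of local treatment and the pathway is narrow. What they show is an undefined case in the primary endpoint of a design in which one response can decide the outcome. It is worth closing because doing so is cheap.

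**What to change.** 1. Reconcile Sections 5.1 and 5.5.2 on which lesions may receive local treatment, and make clear whether the limit in 5.1 covers radiotherapy. Which clinical rule to adopt is for the sponsor.

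2. Whichever is kept, add to Sections 11.1.4 and 13.4.2: once a target lesion has been resected or irradiated on study, later scans cannot newly establish a CR or PR for the primary ORR analysis, and the patient stays in the denominator. A response confirmed before the local treatment counts. A response first documented before it but not yet confirmed may be confirmed only if the fall still meets the PR threshold with the treated lesion held at its last pre-treatment measurement.

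3. Record the date and site of any local treatment on the CRF and give this to the central reader.

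The cost is a short endpoint rule and a CRF entry. The sample size, thresholds and stated operating characteristics do not change. The downside is that an occasional genuine drug response appearing only after local treatment will not be counted, which errs on the conservative side.
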